6.2.2.13 Tumor Tissue Collection and Correlative Studies Blood Sampling

Before and during trial therapy, if a lesion is biopsied or for clinical purposes, a sample will be retained for protocol-related correlative studies. If a patient has had a previous biopsy, the pre-treatment sample may be taken from paraffin-embedded tissue.

6.2.2.13.1 Study-Related Biopsies and Tissue Collection

Tissue from fresh tissue (see below) is required at study entry. Fresh tumor biopsy is required one time after pembrolizumab. These requirements may be waived by the principal investigator.

Tumor tissue will be obtained prior to initiation of study therapy from any primary or locoregional disease site and processed according to the specifications of the lab manual. When a biopsy is being done for standard-of-care clinical purpose, tissue will be obtained from this procedure if available. Otherwise a study-related biopsy will be done.

If the patient undergoes a biopsy at any point during protocol therapy for clinical purpose, extra tumor tissue will be collected for study purposes if available.

6.2.3 Laboratory Procedures/Assessments

Details regarding specific laboratory procedures/assessments to be performed in this trial are provided below. Laboratory Safety Evaluations (Hematology, Chemistry and Urinalysis)

Laboratory tests for hematology, chemistry, urinalysis, and others are specified in Table 5.

Table 5 Laboratory Tests

Hematology	Chemistry	Urinalysis	Other
Hematocrit	Albumin	Blood	Serum β -human chorionic gonadotropin†
Hemoglobin	Alkaline phosphatase	Glucose	(β -hCG)†
Platelet count	Alanine aminotransferase (ALT)	Protein	PT (INR)
WBC (total and differential)	Aspartate aminotransferase (AST)	Specific gravity	aPTT
Red Blood Cell Count	Lactate dehydrogenase (LDH)	Microscopic exam (If abnormal)	Total triiodothyronine (T3)
Absolute Neutrophil Count	Carbon Dioxide ‡	results are noted	Free tyroxine (T4)
Absolute Lymphocyte Count	(CO_2 or bicarbonate)	Urine pregnancy test †	Thyroid stimulating hormone (TSH)
	Uric Acid		
	Calcium		
	Chloride		Blood for correlative studies
	Glucose		
	Phosphorus		
	Potassium		
	Sodium		
	Magnesium		
	Total Bilirubin		
	Direct Bilirubin (If total bilirubin is elevated above the upper limit of normal)		
	Total protein		
	Blood Urea Nitrogen		

† Perform on women of childbearing potential only. If urine pregnancy results cannot be confirmed as negative, a serum pregnancy test will be required.

‡ If considered standard of care in your region.

After Cycle 1, pre-dose laboratory procedures can be conducted up to 72 hours prior to dosing. Results must be reviewed by the investigator or qualified designee and found to be acceptable prior to each dose of trial treatment.

6.2.3.1 Blood Collection for Serum Pembrolizumab

Sample collection, storage and shipment instructions for serum samples will be provided in the Laboratory Manual.

6.2.3.2 Blood Collection for Anti-Pembrolizumab Antibodies

Sample collection, storage and shipment instructions for blood samples will be provided in the Laboratory Manual.

6.2.4 Other Procedures

6.2.4.1 Withdrawal/Discontinuation

When a subject discontinues/withdraws prior to trial completion, all applicable activities scheduled for the final trial visit should be performed at the time of discontinuation. Any adverse events which are present at the time of discontinuation/withdrawal should be followed in accordance with the safety requirements outlined in Section 6.3 - Assessing and Recording Adverse Events. Subjects who a) attain a CR or b) complete 12 months of treatment with pembrolizumab may discontinue treatment. After discontinuing treatment following assessment of CR, these subjects should return to the site for a Safety Follow-up Visit (described in Section 6.2.5.3.1) and then proceed to the Follow-Up Period of the study (described in Section 6.2.5.3.2).

6.2.5 Visit Requirements

Visit requirements are outlined in Section 6.0 - Trial Flow Chart. Specific procedure-related details are provided above in Section 6.2 - Trial Procedures.

6.2.5.1 Screening Period

Prior to initiation of study therapy, the patient will require a screening visit. Scans, and evaluations should be done as close to the initiation of therapy as feasible, and no more than 28 days prior. Laboratory studies should be completed within 14 days of initiation of therapy. In some cases labs will need to be repeated if screening lasts longer than 14 days. The following should be addressed at the screening visit:

1. Informed Consent
2. Medical History
3. Complete physical examination, vital signs, and measurement of height and weight
4. Review of prior and concomitant medications
5. CT scan of chest, abdomen and pelvis

6. ECOG Performance status evaluation
7. Determination of baseline adverse event status
8. Pregnancy test for women of childbearing potential, and counseling that sexually active women of childbearing potential must use an effective form of birth control during the entire study period
9. Determination of sufficient tumor specimen for evaluation of PD-L1 status
10. Laboratory studies: CBC with differential, serum chemistries, liver function tests, LDH, TSH, T3 and Free T4, PT/INR and PTT, uranalysis
11. Collection of blood, fresh (within 6 weeks) tissue and archival tissue for correlative studies
12. Evaluation by an ENT

6.2.5.2 Treatment Period

On-study visits will occur on day 1 of each cycle of MK-3475, and will include the following at every visit:

1. Directed physical examination, vital signs, and measurement of weight
2. Review of concomitant medications
3. Performance status evaluation
4. Determination adverse events
5. Laboratory studies: CBC with differential, serum chemistries, liver function tests, LDH
6. TSH and Free T4 will be done every other cycle starting with Cycle 2
7. CT scans of chest, abdomen and pelvis will be done at the end of cycles 2 if clinically indicated and end of cycle 4.
8. Collection of blood at the end of cycle 4 for correlative studies. Collection of and fresh tissue at the end of cycle 4 or at discontinuation if earlier
9. Evaluation by an ENT at the end of cycle 4 or at discontinuation if earlier

After clinically evident progression or if the patient is discontinuing treatment for any reason the patient will be seen for a study visit, at which the following will be addressed:

1. Directed physical examination, vital signs, and measurement of weight
2. Review of concomitant medications
3. Performance status evaluation
4. Determination adverse events
5. Collection of blood for correlative studies, unless end of cycle 4 collection within 21 days. Collection of fresh tissue for correlative studies if not already taken at end of cycle 4 as described above.
6. Evaluation by an ENT
7. CT scans of chest, abdomen and pelvis if not already taken at end of cycle 4

Fresh tumor specimens will be obtained if feasible during therapy if the patient undergoes resection or biopsy for a standard-of-care clinical purpose per the study flow chart.

6.2.5.3 Post-Treatment Visits

6.2.5.3.1 Safety Follow-Up Visit

The mandatory Safety Follow-Up Visit should be conducted approximately 30 days after the last dose of trial treatment or before the initiation of a new anti-cancer treatment, whichever comes first. All AEs that occur prior to the Safety Follow-Up Visit should be recorded. Subjects with an AE of Grade > 1 will be followed until the resolution of the AE to Grade 0-1 or until the beginning of a new anti-neoplastic therapy, whichever occurs first. SAEs that occur within 90 days of the end of treatment or before initiation of a new anti-cancer treatment should also be followed and recorded. Any unexpected SAE that occurs more than 90 days after drug administration but is possibly, probably or definitely attributed to drug administration will be recorded and reported.

6.2.5.3.2 Follow-up Visits

At each follow up visit patients will have a directed physical exam, including ECOG performance status, vital signs and weight. A comment will also be made regarding the post-study anticancer status. Subjects who discontinue trial treatment for a reason other than disease progression will move into the Follow-Up Phase and should be assessed every 8 weeks (± 7 days) with imaging done every 9 weeks (± 7 days). Every effort should be made to collect information regarding disease status until the start of new anti-neoplastic therapy, disease progression, death, or end of the study. Information regarding post-study anti-neoplastic treatment will be collected if new treatment is initiated.

6.2.5.3.3 Survival Follow-up

Once a subject experiences confirmed disease progression or starts a new anti-cancer therapy, the subject moves into the survival follow-up phase and should be contacted by telephone

every 12 weeks to assess for survival status until death, withdrawal of consent, or the end of the study, whichever occurs first.

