3.2 Secondary Objective(s) & Hypothesis(es)

1. To determine changes in PD-L1 expression following irradiation
 - a. Hypothesis- irradiation will increase inflammation and PD-L1 expression
2. To determine the overall response rate as a function of PD-L1 expression
 - a. Hypothesis- higher rates of PD-L1 expression will be associated with higher overall response rates
3. To evaluate median progression free survival and overall survival
 - a. Hypothesis- based on limited data from previous studies the expected rate of DFS and OS are approximately 30% and 50% respectively
4. To determine the rate of immune related adverse events in patients receiving immunotherapy following radiation with or without systemic therapy
 - a. Hypothesis- The rate of immune related events post radiation will be similar to that of the baseline rate receiving immunotherapy in the metastatic setting
5. To determine the rate of distant metastases
 - a. Hypothesis- based on limited data from previous studies the expected rate of distant metastases is approximately 33%

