3.3 Exploratory Objective

1. To determine the relative changes in levels of key immune cells including CD8+ T cells, CD4+ Tcells, Tregs, and FOXP3+ cells following radiation with or without systemic therapy and immunotherapy
2. To determine the baseline values and changes in PD-L1 expression in HPV(-) and HPV(+) tumors
3. To determine changes in PD-L1 expression in patients who received radiation alone, versus radiosensitizer based radiation
4. Rate of distant metastases

5. To examine PD-1/PD-L1 expression, tumor infiltrating lymphocytes, and other immune markers in responders to pembrolizumab, to define an immune signature predictive of post radiation response to the drug.

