The presence of residual disease following definitive radiation/chemoradiation is an established prognostic marker for worsened disease specific survival in HNSCC patients¹⁴. In a 65 patient experience from Fox Chase Cancer Center, 43% of patients undergoing planned neck dissection for initial N2-N3 neck disease following chemoradiation were found to have persistent disease. This was associated with worsened locoregional control, recurrence free and overall survival¹⁵. The 3-year recurrence free survival rate in patients with positive residual neck disease was 37% in comparison to 85% in patients with no evidence of residual cells ($p = 0.002$). In a separate series of 35 patients with oropharyngeal carcinoma with clinical or radiographic evidence of residual neck disease, viable cancer cells were found in 68% of specimens. Of these, despite undergoing surgical resection of all known disease, 42% developed local recurrences, 29% developed regional recurrences and 25% failed distantly. Overall the 5-year disease specific survival was nearly 100% in patients without residual disease, but only 55% in patients with viable tumor cells¹⁴. A study from MSKCC looking at 56 patients who had neck dissections following chemoradiation demonstrated that 33% had viable tumor in their neck dissection specimens, and the 5-year overall survival (OS), disease specific survival (DSS), and relapse free survival (RFS) were worse in patients with viable tumor in their specimens (OS 49% vs. 93%, $p = 0.0005$; DSS 56% vs. 93%, $p = 0.003$; RFS 30% vs. 75% $p = 0.004$)¹⁶. In patients with residual tumor cells, 63% developed recurrence, with 26% recurring locally, 19% recurring regionally, and 42% recurring distantly. Taken together, the results suggest that even in patients successfully salvaged with surgery, patients with viable tumor cells following radiation still have a worsened prognosis and are at high risk for local, regional, and distant failure suggesting alternative strategies for escalating therapy are needed.

Rationale for immunotherapy

Curative therapy for head and neck cancer has historically depended on surgery and/or radiation, and for patients with persistent or recurrent disease following initial curative therapy,

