5.8 Subject Withdrawal/Discontinuation Criteria

Subjects may withdraw consent at any time for any reason or be dropped from the trial at the discretion of the investigator should any untoward effect occur. In addition, a subject may be withdrawn by the investigator or the Sponsor if enrollment into the trial is inappropriate, the trial plan is violated, or for administrative and/or other safety reasons. Specific details regarding discontinuation or withdrawal are provided in Section 6– Other Procedures.

A subject must be discontinued from the trial treatment for any of the following reasons:

- The subject or legal representative (such as a parent or legal guardian) withdraws consent.
- Confirmed radiographic disease progression
- Unacceptable adverse experiences as described in Section 5.2.1.2
- Intercurrent illness that prevents further administration of treatment
- Investigator's decision to withdraw the subject
- The subject has a confirmed positive serum pregnancy test
- Noncompliance with trial treatment or procedure requirements
- The subject is lost to follow-up
- Completed 12 months of uninterrupted treatment with pembrolizumab or 17 administrations of study medication, whichever is later.
- *Note: 12 months of study medication is calculated from the date of first dose.*
Administrative reasons

The End of Treatment and Follow-up visit procedures are listed in Section 6 (Protocol Flow Chart) and Section .6.2.5 (Visit Requirements).

From the administration of first treatment until 30 days (unless otherwise specified) subsequent to last treatment or withdrawal of subject, new onset adverse events will be captured. Follow-up and reporting of these events will follow the same procedure as for AEs observed during the study period. Serious Adverse Events will be collected for 90 days after the end of treatment as described in Section 6.3. In addition, any unexpected SAE that occurs more than 90 days after drug administration but is possibly, probably or definitely attributed to drug administration will be recorded and reported.

Subjects who discontinue for reasons other than progressive disease will have post-treatment follow-up for disease status until disease progression, initiating a non-study cancer treatment, withdrawing consent or becoming lost to follow-up. After documented disease progression each subject will be followed by telephone for overall survival until death, withdrawal of consent, or the end of the study, whichever occurs first.

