1. In the case that a patient initiates a subsequent anti-cancer therapy the 30 day follow up should occur prior to the first dose of the new therapy and patients will move to survival follow up.
2. Vital signs should include temperature, pulse, respiratory rate, weight and blood pressure. Height will be measured at screening only.
3. Vital signs will be taken prior to the administration of each dose of trial treatment and at discontinuation of each treatment.
4. ECOG status will be evaluated prior to the administration of each dose of trial treatment and at discontinuation of each treatment.
5. Screening lab will be assessed within 14 days of first treatment.
6. After cycle 1, pre-treatment labs can be drawn up to 72 hours pre-dose.
7. The baseline CT scan can be from before study enrollment as long as the scan is within 4 weeks of study treatment.
8. Archival tissue from a biopsy prior to radiation treatment with or without systemic therapy should be requested.
9. All patients will have a biopsy prior to the start of study treatment. This specimen may be obtained up to 6 weeks (42 days) prior to initiation of treatment on Day 1 and following completion of RT/CRT. This pre-treatment biopsy can be used to confirm residual disease.
10. Patients will have a research biopsy after completion of the 4th treatment cycle or at study discontinuation if they come off treatment before cycle 4. There will be no additional biopsy for patients who stay on treatment past 4 cycles.
11. Imaging during study treatment cycles will occur at the end of cycle 2 when clinically indicated and cycle 4 or at disease progression whichever comes first (required). Less frequent imaging is acceptable during the continuation cycles, although a minimum of every 8 weeks is recommended.
12. If a patient comes off trial for reasons other than disease progression imaging should be done every 9 weeks ±7 days
13. Information on SAEs will be collected for 90 days after the end of treatment. Any unexpected SAE that occurs more than 90 days after drug administration but is possibly, probably or definitely attributed to drug administration will be recorded and reported.
14. Patients will have a repeat ENT evaluation for resectability status after completion of the 4th treatment cycle or at study discontinuation if they come off treatment before cycle 4. There will be no additional ENT evaluation for patients who stay on treatment past 4 cycles

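### Distant metastases that appear after a locoregional first progression have no planned collection, so the rate for secondary objective 5 is only a lower bound

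*Combined protocol and SAP*

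**What the plan says.** Section 3.2 makes the rate of distant metastases secondary objective 5 and attaches an expectation: "based on limited data from previous studies the expected rate of distant metastases is approximately 33" per cent. It does not name the studies, give a time point, or say whether the figure means metastasis as first failure or at any time. Section 3.3 lists the item again as exploratory ("Rate of distant metastases"). Section 7.1 gives it no definition and no analysis.

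Four places govern what is collected after treatment:

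- Section 6.2.5.3.3: "Once a subject experiences confirmed disease progression or starts a new anti-cancer therapy, the subject moves into the survival follow-up phase". Contact is then by telephone, "every 12 weeks to assess for survival status until death, withdrawal of consent, or the end of the study, whichever occurs first".
- Section 5.8: "After documented disease progression each subject will be followed by telephone for overall survival until death".
- Section 6.2.5.3.2: "Every effort should be made to collect information regarding disease status until the start of new anti-neoplastic therapy, disease progression, death", or the end of the study.
- Section 6.1, flow chart note 12: "If a patient comes off trial for reasons other than disease progression imaging should be done every 9 weeks".

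None of these separates local, regional and distant progression. The flow chart also has a row for post-study anticancer therapy, marked in two late columns that appear to be follow-up and survival follow-up. That row records treatment, not the site of disease.

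**The concern.** Patients enter with biopsy-proven disease at the primary site or in the neck and with no distant disease on CT (section 5.1.1). Locoregional progression is therefore a foreseeable first event. Take a patient whose neck disease progresses at the end of cycle 2 and who develops lung metastases some months later. The progression moves this patient to telephone follow-up, and no procedure or data item then asks about the lung metastases.

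The objective is worded as the rate of distant metastases, without restriction to first failure, and it carries a numerical expectation. In a single-arm study, a low count produced by the follow-up rule would look the same as a low count produced by the drug. The error runs only one way, towards the favourable reading.

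**Working it through.** **1. The plan's own figure.** The 33% has no stated inputs, so it cannot be reproduced. Section 4.2.1 gives distant-failure rates of 25% and 42% in two series of patients with residual tumour. Their midpoint, (25 + 42)/2 = 33.5%, is close, but nothing in the documents says that this is the source.

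**2. What the schedule captures.**

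| Situation | Planned collection |
|---|---|
| Metastasis at or before first progression | Yes: CT at progression (6.2.2.12) and at the discontinuation visit if not already done (6.2.5.2); a new lesion counts as progression (6.2.2.12.1) |
| Off treatment without progression, no new therapy | Yes: imaging every 9 weeks (6.2.5.3.2; flow chart note 12) |
| Metastasis after confirmed locoregional progression, off drug | None |
| Unresectable, radiographic progression with clinical benefit | Section 2.1 allows continued drug, hence scans; sections 5.3 and 5.8 tie progression to stopping. These passages must be reconciled |

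Safety reporting does not fill the gap. Section 6.3 does not count progression of the study cancer as an adverse event unless it is judged drug related, and section 6.3.3.1 leaves deaths from progression out of the serious-event rule.

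Starting a new anticancer therapy triggers the same switch (6.2.2.6.3, 6.2.5.3.3). The text does not say whether protocol surgery counts as such.

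Hence: observed rate = ever-metastasis rate − share first seen after the switch, which is at most the ever-metastasis rate.

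**3. How much distant failure coexists with locoregional failure.** Only the 56-patient neck-dissection series in section 4.2.1 allows a check. Among its patients with residual tumour, "63% developed recurrence, with 26% recurring locally, 19% recurring regionally, and 42% recurring distantly".

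- Sum of sites: 26 + 19 + 42 = 87%, against 63% with any recurrence. Overlap: 87 − 63 = 24 points.
- Local or regional failure (U) lies between 26% (regional wholly inside local) and 26 + 19 = 45% (no overlap).
- Distant together with locoregional failure = 42 + U − 63. With U = 26 this is 5 points; with U = 45 it is 24 points.

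So 5 to 24 of the 42 points were distant failures in patients who also failed locoregionally. The order of events is not given. If none of these were locoregional first, the rule would miss 0 points; if all were, up to 24 points, or 24/42 = 57% of distant failures.

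**4. Effect on the count.** Let f be the share of distant metastases first appearing after the switch. The documents give no value, so f is an assumption. Captured rate = 33% × (1 − f), with n = 24.

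| f (assumed) | Captured rate | Expected events | Shortfall |
|---|---|---|---|
| 0 | 33.0% | 7.9 | 0 |
| 0.10 | 29.7% | 7.1 | 0.8 |
| 0.25 | 24.8% | 5.9 | 2.0 |
| 0.50 | 16.5% | 4.0 | 4.0 |

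**5. Reading the result.** With a true 33% fully captured, the binomial probability of 4 or fewer events in 24 is 0.06. With f = 0.50 it is 0.64. Precision is poor in any case: the exact 95% interval is 15.6% to 55.3% for 8/24 and 4.7% to 37.4% for 4/24.

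**The case against.** The strongest reply is that no undercount has been demonstrated. The range in step 3 starts at 0 and its ceiling needs every overlapping distant failure to be both later and locoregional first. The residual-tumour group in that series is about 0.33 × 56 = 18 patients, so 24 points is roughly four of them. The other series (42% local, 29% regional, 25% distant) gives no total for any recurrence, so overlap cannot be checked there. All of this stands. It limits what can be said about size; it does not supply the missing data collection.

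A reader might go further in three ways that the documents do not support:

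- *That later metastases are never counted.* A site may learn of one by telephone, and some unresectable progressors may stay on drug and be scanned under section 2.1. What is absent is planned collection.
- *That locally progressing patients will be coded as free of distant disease.* No section says how they would be coded. They could equally be censored or treated as having a competing first failure.
- *That the result is biased low against the 33% because that figure comes from series counting overlapping sites.* Its source is not stated, and it may be on either basis.

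It is also fair that consequences are limited. The item is listed as both secondary and exploratory, is absent from the secondary endpoints named in sections 2.1 and 7.1, and has no planned test. Metastasis as first failure is a legitimate endpoint, but objective 5 does not say that this is what it means.

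**Conclusion.** The point holds. Following the plan as written, distant metastases first appearing after a confirmed or documented locoregional progression are not systematically recorded, and the observed rate is a lower bound on the ever-metastasis rate. This is a stated follow-up rule that falls short of a stated objective, not just a missing detail.

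The size cannot be fixed. On the one series that allows a check, the undercount could be anything from 0 to 24 points, assuming that its failure pattern carries over to this population. The event counts under f are illustrations on assumed values.

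Nor can the rate be set against 33% with confidence, because the basis and horizon of that figure are unknown. The stated trial duration is 18 months (section 1.0), whereas the series used in step 3 reports 5-year outcomes. The primary response-rate analysis is unaffected. The gap is worth closing because it is cheap to close and the error has one direction.

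**What to change.** In section 6.2.5.3.3 and the flow chart, add to the existing 12-weekly contact: distant metastasis yes/no, date and site, taken from the treating record. In section 7.1, define the endpoint, report the cumulative incidence of distant metastasis at a stated time point with death as a competing event, and report distant metastasis as first failure separately.

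The new field does not by itself make the 33% comparison like for like. In either case, state the basis and time horizon of the 33% or drop the comparison. If the field is not added, restate objective 5 as distant metastasis as first failure and remove the 33% comparison. Reconcile section 2.1 with sections 5.3 and 5.8 so that it is clear which progressing patients continue to be scanned.

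Cost: a short addition to the case report form and a few sentences in the protocol, with no extra imaging. The downside is that later metastases will be clinically ascertained, not found on a fixed scan schedule, so their dates will be less exact and some silent ones will still be missed.
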